## 1. OVERVIEW OF THE TREATMENT PLAN

### INDUCTION

[figure not shown]

\* Daunorubicin dose:

- 90 mg/m^2: Age < 60
- 60 mg/m^2: Age  $\geq$  60 or for patients who are <60 and receiving a second cycle of induction (per physician's discretion)

- Crenolanib starts approximately 24-48 hours after completion of Cytarabine (+7-day window). **Normal total bilirubin and ALT and AST  $\leq$  2.0x ULN are required within 24 hours prior to crenolanib commencement. Crenolanib can be delayed until these criteria are met.** (If crenolanib will be delayed longer day 16, a discussion with PI and sponsor should be conducted to determine the best options for the patient)
- On first day of crenolanib, only one 100 mg dose given; from second day on, all three doses given (100 mg TID)
- A total of two cycles of induction will be allowed.
- Crenolanib should be held 72 hours prior to subsequent chemotherapy

### CONSOLIDATION

- Cytarabine dose:
  - Age < 60: 3000 mg/m^2 (3g/m^2)
  - Age  $\geq$  60: 1000 mg/m^2 (1 g/m^2)
- On days 1,3,5 every 12 h (total of 6 doses)
- Up to 4 cycles of consolidation allowed with HiDAC

- Crenolanib starts approximately 24-48 hours after completion of cytarabine (+7-day window).
- **Normal total bilirubin and ALT and AST  $\leq$  2.0x ULN are required within 24 hours prior to crenolanib commencement. Crenolanib can be delayed until these criteria are met.** (If crenolanib will be delayed longer day 14, a discussion with PI and sponsor should be conducted to determine the best options for the patient)
- Crenolanib should be held 72 hours prior to subsequent chemotherapy

## MAINTENANCE

Crenolanib 100 mg TID (or last tolerated dose during induction/consolidation) PO starting on Day 1 continuously for 28 day cycles

D1

D28

- A total of 12 cycles of maintenance will be allowed.
- During maintenance, patients will take continuous crenolanib. Cycles will be 28 days long.
- Patients who have received HSCT and remain in remission may receive crenolanib maintenance therapy. Crenolanib should be restarted no sooner than 30 days post-HSCT and should be administered at the same dose of crenolanib last taken by the patient.
- Patients not undergoing hematopoietic stem cell transplant who are in remission may continue on crenolanib after induction and/or HiDAC consolidation.

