### **7.4. Discontinuations**

#### **7.4.1. Discontinuations of Study Drugs and Disease status/Survival Follow up of Patients**

The criteria for enrollment must be followed explicitly. If a patient who does not meet enrollment criteria is inadvertently enrolled, that patient should be immediately discontinued from the study drug.

Study drug may be held for an extended period of time for comorbidities including but not limited to infections, ICU admissions, severe graft vs host disease, and other comorbidities typically seen in patients undergoing induction, consolidation or allogeneic transplant therapies for AML. Such prolonged drug hold will not require the patient to be taken off study. Study drug can be restarted, even after prolonged drug holds, at the same dose as was last received by the patient. Restart of study drug will require a discussion with the sponsor.

Study drug may be held for an extended period of time if requested by the patient without necessitating the patient to be taken off study. Study drug can be restarted, even after prolonged drug holds, at the same dose as was last received by the patient. Patients will be continued to be followed for survival and disease status per protocol. Safety will be followed as per section 14.

Patients, who for any reason, require treatment with another therapeutic agent for AML or investigational agent will be discontinued from the study drug prior to introduction of the new agent. Restart of study drug will require a discussion with the sponsor.

Patients who have disease refractory to induction or consolidation therapy will be taken off crenolanib but be followed for survival. Similarly, patients who relapse after achieving a response will be taken off crenolanib but be followed for survival.

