### 8.2.2. Consolidation

Therapy with crenolanib will be held for 72 hours prior to the start of the first dose of cytarabine given for consolidation. Crenolanib treatment should be continued during the period of marrow recovery.

Subjects on both cohorts A and B may have up to 4 consolidation courses with:

- High dose cytarabine (HiDAC) given as 3 g/m^2 ( $<$ 60 years old) or 1 g/m^2 (for  $\geq$ 60) intravenously over 3 h every twelve hours on days 1, 3, 5 (total of 6 doses).

Crenolanib will start approximately 24-48 hours after completion of cytarabine (+7 day window). Adequate liver function including normal total bilirubin ALT and AST  $\leq$ 2.0x ULN are required within 24 hours prior to crenolanib commencement. Crenolanib can be delayed until this criterion is met (If crenolanib will be delayed longer day 14, a discussion with PI and sponsor should be conducted to determine the best options for the patient).

- Dose of crenolanib will be the same as that given in induction(s).
- Dose modification of crenolanib is allowed based on treating physician discretion according to Section 8.4 of this protocol.

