### 8.2.3. Maintenance

Subjects not undergoing hematopoietic stem cell transplant who are in remission may continue on crenolanib after induction and/or HiDAC consolidation. Following the last dose of cytarabine given for consolidation, crenolanib can be given continuously for an additional twelve cycles.

Patients who undergo allogeneic transplant may receive maintenance crenolanib after transplant if they fulfill prerequisites. Subjects in remission who are scheduled for allogeneic hematopoietic stem cell transplant (HSCT) should discontinue crenolanib at least 72 hours prior to start of conditioning therapy. Start of maintenance therapy is intended no sooner than 30 days after allogeneic HSCT.

Prerequisites for start of maintenance are:

- a stable dose of immunosuppressive drugs for management or prophylaxis of GVHD or
- no escalation of therapy for GVHD within 14 days of starting study drug
- have no more than grade 2 persistent non-hematological toxicity related to the transplant
- must have received crenolanib during induction for AML prior to HSCT to continue on to maintenance

Maintenance therapy, whether following transplant or not will start at the last dose tolerated during induction/consolidation therapy. For example, if the patient was taking 80 mg TID prior to proceeding with HSCT, maintenance therapy will resume at 80 mg TID. If well tolerated, crenolanib can be escalated to 100 mg TID. Crenolanib maintenance can be given for up to 12 cycles and additional therapy can be provided after discussion with the sponsor.

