**Table 5 Crenolanib dose reduction for non-hematologic toxicities related to crenolanib**

Toxicity (CTCAE v4.03)	Dose Modification
Grade 1 or 2	No dose modification
Grade 3 or 4 (except nausea, vomiting or diarrhea)	Hold drug until toxicity resolves to grade 1 or less. Restart drug at next lower dose level (see Table 4)
Grade 3 or 4 nausea, vomiting or diarrhea despite optimal therapy within 72 hours of onset	Hold drug until toxicity resolves to grade 1 or less. Restart drug at next lower dose level (see Table 4)

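### For a patient transplanted while a crenolanib toxicity hold is still open, the protocol gives conflicting restart doses one dose level apart and does not say which governs

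*Combined protocol and SAP*

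**What the plan says.** Three rules bear on the dose at which crenolanib resumes after transplant.

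- **Dose last taken.** In Section 1, Maintenance, the bullet on transplanted patients in remission says crenolanib "should be administered at the same dose of crenolanib last taken by the patient".
- **Dose last tolerated.** The header line of that same part of Section 1 gives 100 mg TID "or last tolerated dose during induction/consolidation". Section 8.2.3 agrees: "Maintenance therapy, whether following transplant or not will start at the last dose tolerated during induction/consolidation therapy". Its only worked example is that "if the patient was taking 80 mg TID prior to proceeding with HSCT, maintenance therapy will resume at 80 mg TID".
- **Next lower level.** For crenolanib-related grade 3 or 4 non-hematologic toxicity, Table 5 says "Hold drug until toxicity resolves to grade 1 or less. Restart drug at next lower dose level (see Table 4". Table 6 (bilirubin above 1.5 x ULN) and Table 7 (ALT or AST above 3 x ULN, alkaline phosphatase above 2.5 x ULN) follow the same pattern. They add a fixed label: (-1) for the first event and (-2) for an event after re-challenge.

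Table 4 sets the levels at 100, 80 and 60 mg TID.

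**The concern.** Each rule reads sensibly alone. They part company only when the last dose taken was one the patient did not tolerate and no lower dose was started before transplant. For that patient, Section 1 points back to the dose that led to the hold, while the tables point one level down.

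The protocol makes this path possible. The synopsis says eligible patients should go to allogeneic transplant. Section 8.2.3 stops crenolanib at least 72 hours before conditioning and intends maintenance no sooner than 30 days after transplant. Transaminitis is listed among the common adverse events (Sections 3.1 and 5.8), and Table 7 requires a stop from grade 2. The prerequisites for maintenance in Section 8.2.3 cover GVHD treatment, transplant-related toxicity and prior crenolanib in induction. They do not mention the crenolanib toxicity behind an open hold. Section 14.6 suspends safety follow-up from the start of conditioning until crenolanib restarts.

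Safety and tolerability is a primary objective. Two sites could re-expose similar patients at different doses, each complying with the protocol. Recurrence of toxicity and dose-reduction rates in post-transplant maintenance would then partly reflect which section the site had read.

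**Working it through.** No sample size, power or error rate is involved, so there is no planned figure to reproduce. The check applies each rule literally to defined patients. An open hold here means that crenolanib was stopped for related toxicity under Tables 5 to 7 and had not been restarted when conditioning began.

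Daily doses from Table 4: 3 x 100 = 300 mg; 3 x 80 = 240 mg; 3 x 60 = 180 mg.

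| Patient | Section 1 bullet (last taken) | Section 1 header and 8.2.3 (last tolerated) | Tables 5 to 7 (next lower level) |
|---|---|---|---|
| A. Held at 100 mg TID, the only dose ever taken; transplanted before restart | 100 mg TID | Undefined | 80 mg TID |
| B. Reduced to 80 mg TID for toxicity, held again at 80; transplanted before restart | 80 mg TID | Unclear: both doses led to a hold | 60 mg TID |
| C. Held at 100, restarted at 80 and tolerated it; then transplanted | 80 mg TID | 80 mg TID | 80 mg TID, already applied |

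- Patient A: 300 against 240 mg/day. 300/240 = 1.25, so the higher reading is 25% above the lower.
- Patient B: 240 against 180 mg/day. 240/180 = 1.33, so 33% above.
- Patient C: no conflict. This is the situation in the Section 8.2.3 example, so the example does not help with A or B.

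**Labels in Tables 6 and 7.** Patient D has been reduced to 80 mg TID under Table 5 and then has a first bilirubin or transaminase event. The first-event row gives both the words for the next lower level and the label (-1).

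- By the words, one step below the current dose: 60 mg TID (180 mg/day).
- By the label, Table 4 level -1: 80 mg TID (240 mg/day).

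Words and label agree only for a patient whose first event occurs at 100 mg TID. Patient D's ambiguity does not depend on transplant.

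**The case against.** The strongest reply is that Section 1 is an overview, that its own header says last tolerated, and that the Section 8.2.3 example treats the dose being taken as the dose tolerated. On that view, last taken is loose shorthand and Section 8.2.3 governs. This may well be the intent, but it does not settle the case: last tolerated gives no dose for patient A, and nothing says that Section 8.2.3 or the tables override the Section 1 bullet.

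Four broader readings are tempting, and the documents do not support them.

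- *That the restart dose is contradictory after any toxicity hold.* Only Tables 5 to 7 are toxicity-hold rules. Without transplant they give one consistent rule, apart from the label problem.
- *That Section 7.4.1 is a further conflicting rule.* It does say "Study drug can be restarted, even after prolonged drug holds, at the same dose as was last received by the patient", but for holds due to comorbidity or patient request. For comorbidity holds it also requires discussion with the sponsor before restart.
- *That Section 8.2.2 conflicts in consolidation.* It says "Dose of crenolanib will be the same as that given in induction(s"), but the next bullet allows modification under Section 8.4, which contains Tables 5 to 7.
- *That a further event at 60 mg TID has no rule.* Section 8.4.1 caps reductions at two, and the note to Table 4 sends anything lower to sponsor discussion with documented justification. That is a cap with an exception route.

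On the labels, one can answer that the words are operative and that (-1) and (-2) merely follow the usual sequence from 100 mg TID. That is reasonable, but the table prints both and they disagree for patient D.

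The analytic stakes are also limited. Holds and reductions are captured in CRFs (Sections 8.4.2 and 8.5), exposure is summarized (Section 13.8), analyses are descriptive, and the response objective concerns induction, before any post-transplant restart.

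**Conclusion.** The point holds for crenolanib-toxicity holds still open when conditioning starts. For those patients Section 1 and Tables 5 to 7 give doses one level apart (300 against 240 mg/day, or 240 against 180 mg/day), the last-tolerated rule may give none, and no section ranks them. The mismatch between words and label in Tables 6 and 7 also holds, for a patient already at 80 mg TID after a Table 5 reduction (240 against 180 mg/day).

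The conclusion rests on reading each rule literally and on a patient being able to reach conditioning before restarting; the protocol does not exclude this. How many patients would do so cannot be derived: the documents give no rate of toxicity holds open at transplant. A reader might infer that the response estimate or the sample size is affected; neither is. What is at stake is consistent conduct, patient safety and the interpretation of post-transplant dose and toxicity data. It should be corrected.

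**What to change.** Reconcile the Maintenance part of Section 1, Section 8.2.3 and Tables 5 to 7 so that one statement governs restart when a crenolanib-toxicity hold spans transplant, including when only one dose was ever taken. Reconcile the words and the (-1) and (-2) labels in Tables 6 and 7 so that they cannot point to different doses for a patient already reduced under Table 5. Sections 7.4.1 and 8.2.2 need only a cross-reference to that statement. Which dose applies in each case is for the sponsor to decide; this point takes no view.

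The cost is a wording amendment and corrected table text, with no added patients, visits or procedures.

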### 3. SYNOPSIS

#### 3.1. Rationale for the Proposed Study

This study is designed to evaluate the safety and clinical benefit of oral crenolanib besylate given sequentially during standard induction and consolidation chemotherapy in patients with newly diagnosed AML with FLT3 activating mutations. Acute myelogenous leukemia (AML) has a significant resistance to primary chemotherapy with a cure rate of only 30-40%. The prognosis varies according to cytogenetic status. Activating mutations of FLT3 including internal tandem duplication (ITD) mutations within the juxtamembrane domain and single base pair mutations within the tyrosine kinase domain (TKD) of the receptor are the most frequent mutations described in AML, with a prevalence of approximately 24-30%. Despite the presence of these mutations, there is no approved target specific therapy for AML patients who harbor them.

Crenolanib besylate (AR-868,596-26) is an orally bioavailable benzimidazole that was designed to be a selective and potent inhibitor of type III receptor kinases FLT3, PDGFR $\alpha$  and PDGFR $\beta$ . Molecular binding data support that crenolanib is a type I kinase inhibitor that binds preferentially to the active kinase conformation of FLT3. As a result of this property, crenolanib potently inhibits both wild type and constitutively active mutant FLT3 kinase. In vitro studies in cell lines and a xenograft model have shown that crenolanib has higher binding affinity ( $K_d$ ) for and potency ( $IC_{50}$ ) against FLT3 kinase with internal tandem duplication (ITD) and tyrosine kinase domain (TKD) mutations. A saturation mutagenesis screen of FLT3-ITD failed to recover any resistant colonies in the presence of crenolanib at a concentration significantly lower than what has been safely achieved in patients. This high affinity of crenolanib allows it to inhibit aberrant FLT3 signaling at clinically achievable concentrations in AML patients.

Two phase II clinical trials administered single-agent crenolanib to a total of 69 patients with FLT3 mutant AML. Encouraging single-agent activity, safety and PK was observed with crenolanib in this patient population. Amongst 18 evaluable who had relapsed AML patients after chemotherapy or allogeneic stem cell transplant (but who had not received prior FLT3 inhibitors), crenolanib therapy resulted in an overall response rate of 50% (39% CR/CRi and 11% PR). Median overall survival was almost eight months (234 days). The overall response to crenolanib monotherapy was 31% in 36 patients who progressed after a median of three prior regimens (including chemotherapy and FLT3 inhibitors like sorafenib, midostaurin and quizartinib). Crenolanib had a half-life of 7.5hrs and no crenolanib accumulation seen with repeated dosing. Common adverse events (AEs) included nausea/vomiting, transaminitis and fluid retention (majority Grade 1/2) and only 2 patients discontinued crenolanib due to related AEs (fatigue and nausea). No patient acquired a secondary FLT3 mutation at the time of relapse following crenolanib.

For patients with newly diagnosed AML, the standard chemotherapy induction regimen used in this study (7+3, cytarabine and anthracyclines) is considered universally as effective as any other regimen. For this trial, crenolanib will be added to standard induction and consolidation chemotherapy regimens. This study will initially have a safety phase with two cohorts designated by anthracycline: in cohort A daunorubicin will be given at 90 mg/m^2 for patients younger than 60 years of age and 60 mg/m^2 for patients  $\geq$ 60 and in cohort B idarubicin will be given at 12 mg/m^2. Once the safety of the combination has been established an expansion of an additional 72 patients will be initiated. During the expansion, patients will be eligible for either anthracycline regimen per physician's discretion.

### 3.2. Study Synopsis

**Title of Study:** A Study of Crenolanib and Chemotherapy in Patients with Newly Diagnosed Acute Myeloid Leukemia with FLT3 Activating Mutations

**Number of Planned Subjects:** 120

*Approximately 48 patients will be enrolled into two cohorts during an initial safety phase:*

- Cohort A: 24 patients receiving cytarabine/daunorubicin followed by crenolanib
- Cohort B: 24 patients receiving cytarabine/idarubicin followed by crenolanib

Once safety of adding crenolanib to cytarabine/daunorubicin and cytarabine/idarubicin has been established, an expansion phase of 72 additional patients will be treated with either cytarabine/daunorubicin or with cytarabine/idarubicin induction chemotherapy followed by crenolanib to further assess the safety and clinical benefit of the combination.

**Length of Study:** 2-3 years

#### Primary Objectives

- To determine the safety and tolerability of crenolanib given sequentially with chemotherapy for newly diagnosed AML
- To determine the response rate to induction therapy in newly diagnosed AML subjects with FLT3 activating mutations when crenolanib is given sequentially with standard induction/consolidation chemotherapy, including the rates of complete remission (CR), CR with incomplete blood count recovery (CRi), and partial response (PR).

#### Secondary Objectives

- To determine the overall survival (OS) in newly diagnosed AML subjects with FLT3 activating mutations when crenolanib is given sequentially with standard induction/consolidation chemotherapy
- In those patients achieving response, assess parameters of response including: remission duration and relapse-free survival (RFS)
- Pharmacokinetic analysis of crenolanib when given with chemotherapy

#### Exploratory Objectives

To evaluate the impact of crenolanib given in combination with chemotherapy:

- Determine steady-state serum crenolanib concentration
- Identify and correlate specific molecular markers with clinical outcomes
- Determine changes in molecular markers during treatment and their correlations with clinical outcomes
- Measure minimal residual disease (MRD) and correlate with post-remission outcomes

#### Inclusion Criteria:

1. Unequivocal diagnosis of AML based on the WHO classification, excluding acute promyelocytic leukemia
2. No prior therapy for AML, except for hydroxyurea and/or leukapheresis, in this setting is allowed.
3. Subjects with AML evolving from MDS with or without prior MDS therapy with demethylating agents will be allowed in the safety phase only.
4. Subjects must have tested positive for FLT3-ITD and/or other FLT3 activating mutations.
5. Age  $\geq 18$  years will be allowed in the safety phase; during the expansion phase, subjects must be  $\geq 18 - \leq 70$  years of age.

6. ECOG PS 0 – 2
7. Adequate liver function, defined as normal total bilirubin, ALT  $\leq 2.0 \times$  ULN, and AST  $\leq 2.0 \times$  ULN.
8. Adequate renal function, defined as serum creatinine  $\leq 1.5 \times$  ULN or GFR  $> 50 \text{ mL/min}$
9. Negative pregnancy test (serum or urine) for women of childbearing potential (WOCBP).
  - Women considered not of childbearing potential include any of the following: no menses for at least 2 years or menses within 2 years but amenorrheic for at least 2 months and luteinizing hormone (LH) and follicular stimulating hormone (FSH) values within normal range (according to definition of postmenopausal for laboratory used) or bilateral oophorectomy or radiation castration and amenorrheic for at least 3 months or with bilateral tubal ligation.
10. WOCBP must practice contraception. Acceptable methods of contraception are double barrier methods (condoms with spermicidal jelly or foam and diaphragm with spermicidal jelly or foam), oral, depo provera, or injectable contraceptives, intrauterine devices, tubal ligations, and abstention.
11. Male patients (except those with prior surgical contraceptive procedures) with female partners who are of childbearing potential: Recommendation is for male and partner to use effective contraceptive methods, such as latex condoms, during the study.
12. Able and willing to provide written informed consent

**Exclusion Criteria:**

1. Pre-existing liver diseases (i.e., cirrhosis, chronic hepatitis B or C, nonalcoholic steatohepatitis, and sclerosing cholangitis, etc.)
2. Known active CNS leukemia
3. ***During the expansion phase*** subjects with therapy-related AML, AML with prior history of MDS with or without prior HMA therapy or AML in the setting of antecedent hematologic disorder.
4. Subject with concurrent severe and/or uncontrolled medical conditions that may impair the participation in the study or the evaluation of safety and/or efficacy
5. NYHA Class III-IV heart failure, myocardial infarction  $< 6$  months prior to study entry, and/or serious arrhythmia requiring anti-arrhythmic therapy
6. Major surgical procedures within 14 days of enrollment (does not include line placement as needed for chemotherapy administration).
7. Unwillingness or inability to comply with protocol.
8. Concurrent use of other investigational agents.
9. Subjects who are not eligible for standard chemotherapy

